5.8.5.2 Study Drug Accountability

Good clinical documentation practices will be employed to record the receipt, storage conditions, accountability, and use or return of the study drug. The study drug will be stored in a secure location with access to the study personnel who will be managing the storage, dispensing, and accountability of the study drug.

Upon completion or termination of the study, final accountability review by the study monitor, and written authorization from the sponsor, all unused and/or partially used study drug should be returned or destroyed at the study clinic. It is the investigator's responsibility to ensure that the sponsor has provided written authorization for study drug disposal, the disposal process follows the study clinic's standard operating procedures, and appropriate records of the disposal are documented and maintained. No unused study drug may be disposed until fully accounted for by the study monitor (or designee). Documentation of unused study drug should include subject number, medication identity (medication #, period #), date, and quantity of study drug used.

5.8.6 Blinding

The pharmacist (and designated staff member responsible for confirmation of study drug dose) will be unblinded to subject treatment assignment; however, the pharmacist will not perform any study procedures other than study drug preparation and dispensing.

Subjects and staff will be blinded to treatment assignment during confinement. The blind will be maintained through a randomization schedule held by the dispensing pharmacist. Subjects and staff will be informed of a subject's end of study day when discharged from confinement. Subjects and staff will not be informed of the specific treatment arm

assignment. The clinical research nurse will administer the subcutaneous study drug in unit dose containers that are not transparent.

5.8.6.1 Breaking the Blind

The study drug blind will not be broken by the investigator or designee unless information concerning the study drug is necessary for the medical treatment of the subject. For unblinding a subject, the randomization information for unblinding can be obtained by contacting the dispensing pharmacist. The sponsor or medical monitor must be notified immediately if the study drug blind is broken. The date, time, and reason that the blind was broken will be recorded in the source documents. If the blind is broken by the investigator or designee, the study drug must be stopped immediately, and the subject must be withdrawn from the study. Data or specimens already collected from subjects who discontinue prematurely and for whom the blind is broken will be made available for analysis if needed.

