Approximately 72 healthy subjects are planned for enrollment. Up to 14 subjects may be qualified as replacements. Thus, a maximum of 86 subjects will be exposed to study drugs and procedures during the study. Every effort will be made to maintain an approximate 50:50 male to female sex distribution.

Recruitment materials (e.g., internet, radio, and print advertisements, social media posts) will be approved by the local Institutional Review Board (IRB, i.e., Advarra) before telephone screening. Subjects will be offered payment for Screening and participation in the study, but no special incentives are offered.

Study Drugs, Dosage, and Route of Administration:

Repatha (evolocumab) 140 mg/mL solution in a single-use prefilled syringe will be obtained. For the low (21 mg), intermediate low (35 mg), and intermediate high (70 mg) doses, the drug will be measured and reduced to the target dose (Table 5-1). The target dose will be administered to the upper arm subcutaneously.

Praluent (alirocumab) 150 mg/mL in a single-dose prefilled pen will be obtained. For all doses, the drug will be measured and reduced to the target dose (Table 5-1). The target dose will be administered to the upper arm subcutaneously.

For all drugs, standard drug doses or lower doses will be used in this research study. A single dose of the assigned study drug will be administered to each subject during the treatment period.

Study Drugs

- Repatha (evolocumab)
- Praluent (alirocumab)

Reference Drug, Dosage, and Route of Administration:

A placebo subcutaneous injection of equal volume and comparable pH to the diluent for the high dose of each drug will be injected into upper arm subcutaneously.

Inclusion Criteria:

Subjects who meet all the following inclusion criteria will be eligible to participate in the study:

- Subject signs an IRB-approved written informed consent and privacy language as per national regulations (e.g., Health Insurance Portability and Accountability Act authorization) before any study related procedures are performed.
- Subject is a healthy man or woman, 18 to 55 years of age, inclusive, who has a body mass index of 18.5 to 32.0 kg/m2, inclusive, at Screening.
- 3. Subject has a LDL-C level >=100 and <=190 mg/dL inclusive, at Screening.

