5.5. Criteria for Subject Withdrawal

Subjects may withdraw from the study at any time at their own request, or they may be withdrawn by the investigator without the approval of the subject based on the

investigator's clinical judgment. A subject is not required to provide a written request to withdraw from the study; however, a written request is required if a subject withdraws consent for his or her personal data to be used for study-related purposes.

A subject may be discontinued for any of the following reasons:

- AE: The subject has experienced an AE that, in the opinion of the investigator, requires early termination. The appropriate electronic case report form (eCRF) must be completed for each AE. If a subject is discontinued from the study due to an AE, the investigator is required to follow-up with the subject until the event resolves or becomes stable. If a subject dies during the study, the cause of death must be reported as a serious AE (SAE), with an outcome of death noted in the eCRF.
- Protocol Violation: The subject failed to meet protocol entry criteria or did not adhere to protocol requirements, and continued participation poses an unnecessary risk to the subject's health.
- Withdrawal by Subject: The subject (or other responsible individual [e.g., caregiver]) wishes to withdraw from the study in the absence of a medical need.
 - NOTE: Withdrawal due to an AE should not be recorded in the "voluntary withdrawal" category.
- Study Terminated by Sponsor: The sponsor, IRB, FDA, or other regulatory agency terminates the study.
- Pregnancy: The subject is found to be pregnant.
 - NOTE: If the subject is found to be pregnant, the subject must be withdrawn immediately. The pregnancy will be followed-up to term, and the outcome, including any premature termination will be recorded. All live births must be followed for a minimum of 30 days or until the first well-baby visit.
- Other.

NOTE: This category records withdrawals caused by an accidental or a medical emergency, unblinding, and other rare cases. The specific reason should be recorded in the comment space of the eCRF.

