8.3.2 Protocol Violations and Deviations

Any significant protocol deviations that the investigator or study clinic staff believes are of major importance (e.g., incorrect randomizations, subject enrolled but not eligible) should be reported to the sponsor and the investigator's IRB as soon as possible. Significant protocol deviations may include the following:

- Deviations from the inclusion/exclusion criteria that may affect subject safety
- Deviations (omission or delay) of safety monitoring procedures
- Deviations in the administration of the study drug
- Deviations in obtaining informed consent

All subjects who are enrolled and receive the study drug, regardless of whether they have a major protocol violation, must continue to be followed for safety for all follow-up study visits.

U.S. Food and Drug Administration Protocol No. SCR-007

9. Appendix

Table 9-1: Schedule of Events by Time Point

	A SERBISER VERTE (NAMED PLE	ON SERVICE PROPERTY VIVE	TOTAL PROPERTY.	ļ			I	I						Will be to b	OTTAIN OF		THE STATE OF	The same	THE SECTION	A 12 TO SEC. A.	PERSONAL STREET	AR STATE BALL	W. A. S.	STATE OF		
	Screening	Checkin / Baseline										۱	reat	Treatment	Period	8										End of Study
Study Week			1				\vdash	 	H			\vdash	-		 	-	H	2	က		2	9	_		Ξ	Day
Study Day	-21 to -2	7	P _{re}		-			-	-	-	-	4	2	8	4	S	2	7	10 1/2	4 21	1 28	35	5 42	93	70	2, 9 8, 9
Hour			٥	0.5	-	7	6	4	9	80	12	24	\vdash	\vdash			-	\vdash	_	\vdash	-	\vdash	_	_		
Visit	-	2						\vdash	\vdash	-						\vdash	_	 	3	\$	9	7	∞	6	2	8, 9, 11
Outpatient visit	×									-	\vdash						Ê	×	×	×	×	×	×	×	×	×
in House Residency		×	×	×	×	×	×	×	×	×	×	×	×	×	×	×	×	-	\vdash	-	-	-				
in formed Consent	×										_		\vdash	-		_				_	-	\vdash	\vdash		ļ	
Medical History	×	×											_	\vdash		-		_	\vdash	_	_	\vdash	_		ļ	
Targeted Physical Exam			×		×		×			×	-		 		-	_	\vdash			_		-				
Comprehensive Physical Examination	×	×									-	×					Ĥ	×			×					×
Vital signs	×	×			×							×			-		Ĥ	×			×	_	L	_		×
12-Lead ECG	×	×										×				\vdash	  ^	×	_		×			_		×
Cinical Chemistry and Hematology	×	×						H				×			_	\vdash	 ^	×			×	L				×
Urinalysis	×	×														_	_		_							×
HIV Ab, HbsAg, HepC Ab	×																									
SARS CoV2 Molecular Test		×											\vdash	_	_	-										
Urine Drug and Alcohol Screen	×	×							-	H		\vdash				_	^	×	H	L		L				×
Pregnancy Test (females only)	×	×										_														×
FSH (females only)	×												-									_				

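### For a subject unblinded after the single Day 1 dose, Protocol 5.8.6.1 (mandatory withdrawal) conflicts with 8.3.2 (safety follow-up of all dosed subjects at all visits), at the cost of scheduled safety contacts and new-onset AE recording

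*Protocol*

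**What the plan says.** **Protocol 5.8.6.1 (Breaking the Blind).** The investigator or designee may not break the blind "unless information concerning the study drug is necessary for the medical treatment of the subject". If they do, "the study drug must be stopped immediately, and the subject must be withdrawn from the study". The section makes no provision for continued safety visits. It deals only with material collected up to that point: data and specimens from early discontinuers "for whom the blind is broken will be made available for analysis if needed".

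**Protocol 8.3.2 (Protocol Violations and Deviations).** All enrolled and dosed subjects, "regardless of whether they have a major protocol violation, must continue to be followed for safety for all follow-up study visits".

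**Dosing (Protocol Synopsis, Study Drugs).** "A single dose of the assigned study drug will be administered to each subject during the treatment period". It is given on Day 1 (5.8.1).

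**What withdrawal leads to.** Protocol 5.1.2, 5.5.1 and 5.6.4 provide a single early-termination visit with the discharge-day procedures. Under 5.7.4.1.2, AE recording runs from consent to discharge or early termination. The same section keeps possibly or probably related AEs under follow-up until they resolve or stabilise, and all SAEs until resolution.

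**Withdrawal categories (Protocol 5.5).** For a discontinuation due to an AE, "the investigator is required to follow-up with the subject until the event resolves or becomes stable". Unblinding is named under the category Other: "This category records withdrawals caused by an accidental or a medical emergency, unblinding, and other rare cases".

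**The concern.** The stop-drug and withdraw rule is written as if treatment were continuing. Here nothing remains to be stopped once the Day 1 injection has been given, so after dosing the rule acts only on follow-up.

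It also falls on an unfavourable subject. The blind may be broken only for medical treatment, so the person taken out of scheduled visits has a medical problem. Protocol 5.1.3 lists hypersensitivity for both drugs, with serious cases for alirocumab, and 5.7.1.1 schedules drug sampling out to Day 84. An AE that starts after early termination falls outside the recording period, and no scheduled contact remains at which the site would learn of it. Yet 8.3.2, read as written, promises those contacts to every dosed subject. A site facing this situation has two mandatory instructions and no statement of which prevails.

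**Working it through.** **1. The two rules side by side, for a subject dosed on Day 1 and unblinded later.**

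| | Protocol 5.8.6.1 | Protocol 8.3.2 |
|---|---|---|
| Who | Any subject whose blind is broken by the investigator or designee | All enrolled subjects who received study drug |
| Force | Mandatory | Mandatory |
| Consequence | Withdrawn from the study | Followed for safety at all follow-up visits |
| Exception for the other rule | None | None |

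Withdrawing the subject on paper while keeping the visits does not settle it. Under 5.7.4.1.2 AE recording formally ends at early termination, so safety follow-up at those visits would have no recording period.

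**2. Exposure prevented.** Planned doses = 1, on Day 1. Doses remaining after Day 1 = 0. Withdrawal after dosing prevents none.

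**3. Follow-up lost.** Inputs: end-of-study day is 84 for groups D, H and I, 56 for C and G, and 42 for A, B, E and F (Protocol 5.1). Outpatient days after the in-house week are 10, 14, 21, 28, 35, 42, 56, 70 and 84 (5.7.1.1). That is 9 visits, which agrees with the maximum stated in 5.1. Assume that early termination takes place on the day of unblinding.

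- Days of AE recording lost = end-of-study day − day of unblinding.
- Visits lost = outpatient days after unblinding, up to the end-of-study day.

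| Unblinded on | D/H/I (to 84) | C/G (to 56) | A/B/E/F (to 42) |
|---|---|---|---|
| Day 7: days | 84 − 7 = 77 | 56 − 7 = 49 | 42 − 7 = 35 |
| Day 7: visits | 9 | 7 | 6 |
| Day 14: days | 84 − 14 = 70 | 56 − 14 = 42 | 42 − 14 = 28 |
| Day 14: visits | 7 | 5 | 4 |
| Day 35: days | 84 − 35 = 49 | 56 − 35 = 21 | 42 − 35 = 7 |
| Day 35: visits | 4 | 2 | 1 |

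**4. What those visits contain for safety.** As far as Table 9-1 can be read, most are AE and concomitant-medication contacts. After Day 7, examination, vital signs, ECG and chemistry/hematology appear only at about Day 28 and at end of study. Early termination brings the end-of-study set forward. The net loss of examination sets is therefore about one (Day 28) for unblinding between Day 7 and Day 28, and none after Day 28.

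**5. Frequency.** The documents give no unblinding rate and none is assumed here. The counts above are per affected subject, not expected losses for the trial.

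**The case against.** **Withdrawal does not end safety oversight.** A reader might infer that it does, and the documents do not support that. The early-termination visit includes examination, vital signs, ECG and laboratory tests. Known related AEs and all SAEs are followed past it under 5.7.4.1.2. A subject unblinded for a serious hypersensitivity reaction would very probably have an SAE or a related AE, and that event stays under follow-up. This stands, and it limits the loss to scheduled contacts and new-onset events. Even for a new SAE the text is arguable, since the 24-hour reporting duty runs from the site becoming aware and carries no end date. That duty needs a contact through which to become aware.

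**The stop-drug clause is not empty.** Randomization may take place on Day -1 (5.6.3.1, 5.8.3.1), so a blind broken before dosing can prevent exposure. This stands. Such a subject is undosed and outside 8.3.2, so the conflict concerns breaks after dosing only.

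**The category Other.** One might infer that filing unblinding there removes the duty to follow the causative event. Protocol 5.5 does not say so. The primary reason must be recorded (5.5.1), and where that is an AE, the AE follow-up duty applies.

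**8.3.2 may be narrower than it reads.** It sits under protocol violations, and taken without limit it would clash with every withdrawal ground in 5.5, including the subject's own request. It could be meant as subject to 5.5. That is a fair reading, but its grammatical subject is all dosed subjects and the text does not state the limit.

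**Matters that add nothing to the point.** SAP 5 excludes early-termination subjects from PK and PD parameter summaries. This does not contradict 5.8.6.1, because SAP 7 keeps excluded data in the listings, and 5.5.2 allows up to 14 replacements. Pregnancy is a separate ground ("If the subject is found to be pregnant, the subject must be withdrawn immediately") with its own follow-up to term.

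**Conclusion.** The conflict is real for a subject unblinded after dosing. Two mandatory rules give different instructions, and the one that removes the subject prevents no dosing. What is lost is the remaining scheduled safety visits and the recording of new AEs: on Day 14, for example, 70, 42 or 28 days and 7, 5 or 4 visits, depending on the assigned end-of-study day. Those figures assume early termination on the day of unblinding. A later early-termination visit would shorten the loss.

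The severity is minor. Breaking the blind should be rare in a single-dose study of about 72 healthy subjects, known related and serious events remain under follow-up, and few examination sets are affected. The documents do not support a stronger conclusion that an unblinded subject is left without safety oversight, or that an endpoint or estimate is compromised.

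**What to change.** In Protocol 5.8.6.1, confine the stop-drug and withdraw rule to a blind broken before dosing. For a blind broken after dosing, require that the unblinding be documented and that the subject stay in scheduled safety follow-up to the assigned end-of-study day, unless consent is withdrawn or the investigator judges that the visits pose a health risk. Align 5.7.4.1.2 so that AE recording for these subjects runs to that same day. Whether PK and PD samples continue can be left to the sponsor.

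The cost is wording in two sections and no visits beyond those already planned. There are two downsides: AE reports after unblinding are open-label and need a flag in the data, and the site must keep contact with a subject whom it would otherwise have released.

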5.8.7 Treatment Compliance

At Screening, as part of the inclusion criteria, it will be confirmed that subjects are able to comply with the protocol-defined procedure of injecting subcutaneous study drug. All doses of the study drug will be administered in the study clinic either under direct observation of or administered by clinic personnel and recorded in the eCRF. If a subject vomits after dosing, the event will be documented as an AE. The decision to replace any subject who vomits after dosing will be made as described in Section 5.5.2.

5.8.8 Prior and Concomitant Medications

Subjects are prohibited from using any prescription or nonprescription drugs (including aspirin or non-steroidal anti-inflammatory drugs [NSAIDs] and excluding oral contraceptives and acetaminophen) within 14 days or 5 half-lives (whichever is longer), or complementary and alternative medicines within 28 days before the first dose of study drug.

Subjects are also prohibited from currently participating in another clinical study of an investigational drug and may not have been treated with any investigational drug within 30 days or 5 half-lives (whichever is longer) of the compound.

Subjects must be instructed not to take any medications, including over-the-counter products, without first consulting with the investigator.

5.8.9 Subject Restrictions

Subjects are not allowed to use nicotine-containing products (e.g., cigarettes, cigars, chewing tobacco, snuff) within 6 weeks before Screening. In addition, subjects are not allowed to ingest alcohol, xanthine-containing products (e.g., tea, coffee, chocolate, cola),

caffeine, grapefruit, or grapefruit juice for 48 hours before dosing and throughout the study. Subjects are not allowed to use aspirin or NSAIDs within 14 days before the first dose of study drug. Subjects will be asked if they have used any of these substances and their responses will be recorded on the eCRF.

Subjects must be able to tolerate a controlled, quiet study conduct environment, including avoidance of music, television, movies, games, and activities that may cause excitement, emotional tension, or arousal during prespecified times (e.g., before and during ECG extraction windows) throughout the duration of the study.

Subjects must be willing to comply with study rules, including the meal schedule, attempting to void at specified times (e.g., before ECG extraction windows), remaining quiet, awake, undistracted, motionless, and supine during specified times, and avoiding vigorous exercise as directed throughout the duration of the study. Subjects will not be allowed to sleep during any ECG extraction periods.

All subjects will fast overnight for a minimum of 8 hours (no food or fluid except water) before blood collection for tests at check-in, during confinement, and for out-patient visits. Standardized meals will be served at consistent times relative to dosing, and no food or fluids will be served containing caffeine. Outside of meal times, the subjects will only be allowed to intake water, which will be available ad libitum.

5.9. Statistical Methods

5.9.1 Sample Size

Up to 86 healthy subjects will be enrolled (including 14 potential replacement subjects). Subjects will be randomized to one of 9 different active treatment arms (i.e. 8 per treatment arm) and 8 will be randomized to placebo. This sample size was determined empirically based on general sample size requirements for estimating values and variability of primary PD and PK/PD characteristics that can be used to inform the study design and sample size of future biosimilarity studies.

5.9.2 Analysis Populations

The PD and PK populations will include all subjects who receive study drug and have at least 1 estimable PD or PK parameter, respectively, after dosing.

5.9.3 General Statistical Considerations

All data will be presented in data listings. Data from subjects excluded from an analysis population will be presented in the data listings, but not included in the calculation of summary statistics. Demographic and baseline characteristics will be summarized overall and by treatment for all subjects.

5.9.4 Subject Disposition

The number of subjects who enroll in the study and the number and percentage of subjects who complete each assessment will be presented. The frequency and percentage of subjects who withdraw or discontinue from the study and the reason for withdrawal or discontinuation will be summarized.

5.9.5 Demographics and Baseline Characteristics

Descriptive statistics will be used to summarize demographic and baseline subject characteristics. For continuous variables, the mean, median, standard deviation (SD), minimum, and maximum values will be reported. For categorical (nominal) variables, the number and percentage of subjects (or observations) will be reported.

5.9.6 Primary Analysis

5.9.6.1 Pharmacodynamics

Peripheral Blood LDL-C and ApoB_AUEC will be calculated for each subject. For each dose, separate intervals will be used for the AUEC assessment to truncate noise introduced from baseline fluctuations. Maximum decrease from baseline will be determined from all sampled timepoints. For both assessments and biomarkers, measures will be log-transformed and utilize an ANCOVA approach for calculating geometric means and 90% confidence intervals for each treatment. PD parameters of evolocumab and alirocumab will be listed and summarized using descriptive statistics (n, geometric mean, coefficient of variation, minimum, median, and maximum).

Separate population PD analyses will be conducted using nonlinear mixed effect modeling with NONMEM. AUECs calculated for each subject from all doses for a drug and placebo patient will be combined and evaluated assuming a saturating E_{max} relationship to characterize system parameters such as E_{max} and EC_{50} .

